1.2. Schema

1.3. Schedule of Activities (SoA) – Part 1

See Section 7 for further details of study procedures listed in the SoA.

Assessments	Screening ²	Day 1	Days 2-7	Day 14 ⁴	Day 28 ⁵	Discharge / Early Withdrawal ⁷	Follow-up Phone call (D42 & 60 / Early Withdrawal) ^{6,7}	Notes	
Informed consent ³	X								
Eligibility assessment	X								
Thoracic CT scan or chestX-ray	X							Chest X-ray or CT scan must be available at Screening to confirm a diagnosis of pneumonia and eligibility. Record in the eCRF if a CT scan or chest X-ray is done between Screening and Discharge.	
Demography	X								
Medical history	X							At Screening, record the signs and symptoms of COVID-19 at admission, as detailed in the eCRF.	
Daily clinical features of COVID-19 (for non-mechanically ventilated participants)		←----- Daily ¹ -----→						X	Daily review of COVID-19 signs and symptoms, as detailed in the eCRF.
Full physical examination	X					X			
12-lead ECG	X	X				X		Day 1 - record before dosing.	
Weight	X								
Vital Signs: blood pressure, pulse, respiratory rate and temperature	X	←----- Daily ¹ -----→							Day 1 – measure pre-infusion and approximately 1 hour post-infusion. Measure daily AM (at about same time daily), as per standard of care (SoC).
SpO ₂ (for participants not on invasive mechanical ventilation)	X	←----- Daily ¹ -----→							Day 1 - record before dosing. Measure daily AM and PM (at about same times daily), as per SoC.
Concentration of inspired oxygen (FiO ₂) and / or oxygen flow rate (L/min)	X	←----- Daily ¹ -----→							Day 1 - record before dosing. Measure daily AM and PM (at about same times daily), as per SoC.
Ventilation status, ICU admission and discharge, and ICU supportive care	X	←----- Daily ¹ -----→						X	Includes ventilation status (method of non-invasive ventilation or mechanical ventilation). Record participant admission or discharge from the ICU. Record oxygen treatment if used at home.

Assessments	Screening ²	Day 1	Days 2-7	Day 14 ⁴	Day 28 ⁵	Discharge / Early Withdrawal ⁷	Follow-up Phone call (D42 & 60 / Early Withdrawal) ^{6,7}	Notes	
Ordinal scale	X	←===== Daily ¹ =====→						X	Day 1 - record category before randomization (for stratification) . Record daily AM (at about same time daily).
SOFA score (ICU participants ONLY)	X	←===== Daily ¹ =====→							Day 1 - record before dosing. Record daily AM (at about same time daily), as per SoC.

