7.2.2. SpO₂ (for participants not on invasive mechanical ventilation)

SpO₂ should be measured at the timepoints defined in the SoA (Section 1.3 and Section 1.4). Where possible, SpO₂ should be measured "at rest" *i.e.* not having undergone a procedure for at least 5 minutes. When a participant is mechanically ventilated, no SpO₂ value is expected in the eCRF.

Part 2: SpO₂ should be measured once daily in the morning (up to discharge) at approximately the same time as the Ordinal Scale categorisation.

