Change from baseline in FiO₂ will be calculated, for participants up to Day 28. FiO₂ will be summarized as a fraction rather than a percentage for observed data and using a trimmed means approach as specified in the Section 4.4.2.4.

For the trimmed means, if >50% of the participants experience the intercurrent events listed below at any timepoint, then the data will be summarized up to that timepoint only.

If a participant experiences multiple intercurrent events, then the worst response status will be assumed.

If FiO₂ is not recorded but Oxygen Flow Rate is, the FiO₂ will be calculated.

Intercurrent event	Response Status
Death	Non-responder
Discharge from investigator site to advanced facilitated care	Non-responder
Discharge from Investigator Site for any other reason other than advanced facilitated care	Responder
Independence from supplementary oxygen and missing FiO ₂	Responder

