5.4.1.7. Recovery or Improvement Relative to Baseline in Concentration of Inspired Oxygen (FiO₂)

Change from Baseline in FiO₂, calculated as daily average of all assessments. FiO₂ will be analysed using a composite strategy to handle the intercurrent events as below.

Participants will meet the endpoint if they have an improvement relative to baseline in FiO₂ (derived where lower values indicate improvement) or they have recovered (participant is discharged from investigator site for any other reason other than advanced facilitated care or participant is independent from supplementary oxygen and SpO₂ is missing). If FiO₂ is not recorded but Oxygen Flow Rate is, the FiO₂ will be calculated.

Intercurrent event	Response Status
Death	Non-responder
Discharge from investigator site to advanced facilitated care	Non-responder
Discharge from Investigator Site for any other reason other than advanced facilitated care	Responder
Independence from supplementary oxygen and missing SpO ₂	Responder

In addition, change from baseline in FiO₂ will be summarized for participants up to Day 28. FiO₂ will be summarized for observed data and using a trimmed means approach as specified in the Section 5.4.2.4.

For the trimmed means, if >50% of the participants experience the intercurrent events listed above at any timepoint, then the data will be summarised up to that timepoint only.

If a participant experiences multiple intercurrent events, then the worst response status will be assumed.

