5.4.1.8. Recovery or Improvement Relative to Baseline in SpO₂/FiO₂ Ratio

The ratio of SpO₂/FiO₂ will be calculated for each day using date-time matched values. Change from baseline in SpO₂/FiO₂ will be calculated as average of the daily

assessments, for participants who are not invasively mechanically ventilated. It will be analysed using a composite strategy to handle the intercurrent events as described in the individual endpoint sections. If a participant is a non-responder due to an intercurrent event for either SpO₂ or FiO₂ then they will be a non-responder for the ratio.

Participants will meet the endpoint if they have an improvement relative to baseline in SpO₂/FiO₂ ratio (derived where higher values indicate improvement) or they have recovered (the participant is discharged from investigator site for any other reason other than advanced facilitated care or the participant is independent from supplementary oxygen and SpO₂ is missing).

5.4.1.9. Oxygen-free Days up to Day 28

A participant is considered oxygen free on a day if they meet the definition in Section [5.3.1.5](#).

Intermittent data is expected after discharge from investigator site, therefore if participants have discontinued oxygen and have been discharged to a non hospitalised residence, they will be considered to be oxygen-free during the intermittent timepoints.

5.4.1.10. Ventilator-free Days up to Day 28

A participant is considered ventilator-free on a day if they meet the definition for being alive and not invasively mechanically ventilated in Section [5.4.1.3](#).

Intermittent data is expected after discharge from investigator site, therefore if participants have discontinued ventilation and have been discharged to a non hospitalised residence, they will be considered to be ventilation-free during the intermittent timepoints.

5.4.1.11. Time to Resolution of Pyrexia (>48h) up to Day 28

Time from dosing (days) to first resolution of pyrexia (defined as the first day of a >48-hour period with temperature below thresholds below) up to (and including) Day 28:

Location	Pyrexia Threshold	Core Temperature Equivalent
Forehead	>36.3°C	>37.8°C
Axilla	>36.6°C	>37.8°C
Sublingual region	>37.2°C	>37.8°C
Rectum or Tympanic membrane	>37.8°C	>37.8°C
Pulmonary artery branch	>37.8°C	>37.8°C
Bladder	>37.8°C	>37.8°C
Esophagus	>37.8°C	>37.8°C
Nasopharynx	>37.8°C	>37.8°C
Brain	>37.8°C	>37.8°C
Other	>36.3°C (Minimum Pyrexia Threshold)	>37.8°C

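### Part 1 SAP 5.4.1.7 makes recovery on the exploratory FiO₂ endpoint depend on a missing SpO₂ rather than a missing FiO₂

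*SAP*

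**What the plan says.** Part 1 SAP 5.4.1.7 offers two main routes to response. One is an improvement in FiO₂ from baseline, "derived where lower values indicate improvement". The other is recovery: discharge from the investigator site other than to advanced facilitated care, or the state in which the "participant is independent from supplementary oxygen and SpO₂ is missing". The intercurrent-event table in that section gives responder status to "Independence from supplementary oxygen and missing SpO" (that is, SpO₂). A substitute is allowed for the endpoint variable: "If FiO₂ is not recorded but Oxygen Flow Rate is, the FiO₂ will be calculated".

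Section 5.4.1.6, on the SpO₂ endpoint, has the same recovery condition, and there it fits. Section 5.4.1.8, on the SpO₂/FiO₂ ratio, uses it again: "the participant is independent from supplementary oxygen and SpO₂ is missing".

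The Part 2 SAP, in 4.4.1.9, gives the corresponding FiO₂ row as "Independence from supplementary oxygen and missing FiO" (that is, FiO₂).

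**The concern.** A clause that rescues a participant whose endpoint value is missing should be triggered when that endpoint's own variable is missing. Here it is triggered by a different measurement. Section 1.1 (Table 2) and Appendix 2 of the Part 1 SAP say these endpoints were clarified so that recovery forms part of a composite strategy. With SpO₂ in the clause, that aim is missed for one kind of record: a participant who no longer needs oxygen, is still in hospital, has a saturation reading and has no FiO₂ entry.

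Two exploratory responder analyses are at stake (FiO₂ and the ratio). Under 5.4.2.2 they are reported with an odds ratio, confidence interval and p-value. The trimmed-mean summary of change in FiO₂ is also touched. It relies on the same list of intercurrent events and is cut off once more than 50% of participants have had one.

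**Working it through.** **Which variable belongs in the clause.** Three texts can be set side by side:
- Part 1 SAP 5.4.1.6, SpO₂ endpoint: missing SpO₂.
- Part 1 SAP 5.4.1.7, FiO₂ endpoint: missing SpO₂, in both text and table.
- Part 2 SAP 4.4.1.9, FiO₂ endpoint: missing FiO₂.

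The middle one is out of line with both neighbours, which points to a carry-over and not a design choice.

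**When SpO₂ would be missing.** In the Part 1 Schedule of Activities (protocol 1.3), SpO₂ for participants not on invasive ventilation carries the note "Measure daily AM and PM (at about same times daily), as per SoC", until discharge or Day 28. Protocol 7.2.2 adds: "When a participant is mechanically ventilated, no SpO₂ value is expected in the eCRF". Mechanical ventilation cannot coincide with being off oxygen. So SpO₂ should normally be present in an inpatient off oxygen, and the clause should rarely apply.

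**Literal application.** Take a participant who is alive, in hospital and off oxygen. FiO₂ counts as available if it is recorded or can be calculated from flow rate.

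| SpO₂ | FiO₂ | Rule as written | Rule with missing FiO₂ |
|---|---|---|---|
| recorded | missing | not recovered; improvement not assessable | responder |
| recorded | available | responder by improvement, if below baseline | same |
| missing | missing | responder (recovered) | responder |
| missing | available | responder (recovered) | responder by improvement, if below baseline |

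Rows 1 and 3 differ only in whether SpO₂ was recorded, yet only row 3 is a responder. The correction changes row 1 alone, provided an FiO₂ recorded off oxygen is below baseline.

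**How row 1 is scored.** In the trimmed-mean summary (5.4.2.4), a missing value with no listed event or withdrawal is treated as missing at random and left out of the trimmed count. For the binary analysis the SAP is silent. The missing-data rules in 5.1.5 cover primary and secondary endpoints. Appendix 3 (6.3.1) describes imputation for binary endpoints in general, but its specification table has no FiO₂ row.

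**What size would depend on.** Let f be the share of an arm in row 1, and p the response rate with those participants counted as responders.
- Scored as non-responders: the rate becomes p − f.
- Excluded: the rate becomes (p − f)/(1 − f).
- Imputed with mean response probability q: the rate falls by f(1 − q).

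The documents give neither f nor p. Purely as an assumption, take p = 65% on otilimab and 60% on placebo, a true difference of 5 points.
- f = 15% on otilimab, 10% on placebo. Non-responder scoring: 50% v 50%, difference 0, understated by 5 points. Exclusion: 50/85 = 58.8% v 50/90 = 55.6%, difference 3.3, understated by 1.7 points.
- f = 10% on otilimab, 15% on placebo. Non-responder scoring: 55% v 45%, difference 10, overstated by 5 points. Exclusion: 55/90 = 61.1% v 45/85 = 52.9%, difference 8.2, overstated by 3.2 points.

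The size depends on the unstated scoring rule, and the sign depends on which arm has more row 1 records.

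**The ratio endpoint.** Section 5.4.1.8 forms the ratio from date-time matched SpO₂ and FiO₂, so either one missing leaves no ratio. Its recovery clause covers only missing SpO₂. It takes its event handling from the individual sections, so it also inherits the 5.4.1.7 row. Here the clause is incomplete rather than misplaced.

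**The case against.** The strongest reply is that the problem record may hardly occur. In the Part 1 Schedule of Activities, FiO₂ and/or oxygen flow rate has the same twice-daily note as SpO₂, and no exemption for participants off oxygen. If sites follow it, an FiO₂ or a flow rate exists and the participant can qualify through improvement. This stands as a limit on impact. It does not make the clause right, and the Part 2 row shows that the sponsor foresaw FiO₂ being missing in a participant off oxygen.

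A reader might infer more: that every inpatient off oxygen with a measured SpO₂ is lost, that the response rate falls by the full share affected, and that a benefit of otilimab is therefore understated. The documents do not support this. Only records lacking both FiO₂ and flow rate change status. In the 5.4.1.7 table, only death and discharge to advanced facilitated care are non-responder states, and nothing scores a missing FiO₂ as non-response. Nor is the direction settled. An arm that comes off oxygen sooner may also be discharged sooner, and discharge other than to advanced facilitated care already counts as response, so that arm could have fewer such records.

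Two further limits stand. The Part 2 section is a change-from-baseline summary with no responder endpoint, so it is evidence of intent and not an exact counterpart. Further data-handling conventions are placed in the Output and Programming Specification, which is not among the documents.

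**Conclusion.** The recovery rule in 5.4.1.7 is wrong as written. It makes responder status depend on the absence of a measurement that is not the endpoint, and it leaves unclassified a participant who has come off oxygen. This follows from the text alone and needs no assumption beyond literal application.

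The practical size is unknown. It would be nil if every inpatient off oxygen had an FiO₂ or flow rate entered and the resulting FiO₂ was below baseline. Otherwise it depends on how often FiO₂ is blank off oxygen and on a scoring rule the SAP does not state. No between-arm bias, in either direction, is established. The endpoint is exploratory and the primary and secondary analyses do not use it. The correction is still worth making, because this is an operative endpoint definition and costs almost nothing to repair.

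**What to change.** In Part 1 SAP 5.4.1.7, replace SpO₂ with FiO₂ in the recovery clause and in the last row of the intercurrent-event table, in line with Part 2 SAP 4.4.1.9. In 5.4.1.8, extend the recovery clause to the case where SpO₂ or FiO₂ is missing, since the ratio needs both; the Part 2 SAP has no ratio endpoint to copy from.

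It would also help to state how any FiO₂ value still missing is scored in the binary analysis, and to report by arm how many records were off oxygen, in hospital, with SpO₂ but no FiO₂ or flow rate. That count would show whether the wording mattered.

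The cost is a one-word change in the clause and table row of 5.4.1.7, a short addition in 5.4.1.8 and a matching check of the program. No new data are needed.

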5.4.1.8. Recovery or Improvement Relative to Baseline in SpO₂/FiO₂ Ratio

The ratio of SpO₂/FiO₂ will be calculated for each day using date-time matched values. Change from baseline in SpO₂/FiO₂ will be calculated as average of the daily

assessments, for participants who are not invasively mechanically ventilated. It will be analysed using a composite strategy to handle the intercurrent events as described in the individual endpoint sections. If a participant is a non-responder due to an intercurrent event for either SpO₂ or FiO₂ then they will be a non-responder for the ratio.

Participants will meet the endpoint if they have an improvement relative to baseline in SpO₂/FiO₂ ratio (derived where higher values indicate improvement) or they have recovered (the participant is discharged from investigator site for any other reason other than advanced facilitated care or the participant is independent from supplementary oxygen and SpO₂ is missing).

5.4.1.9. Oxygen-free Days up to Day 28

A participant is considered oxygen free on a day if they meet the definition in Section [5.3.1.5](#).

Intermittent data is expected after discharge from investigator site, therefore if participants have discontinued oxygen and have been discharged to a non hospitalised residence, they will be considered to be oxygen-free during the intermittent timepoints.

5.4.1.10. Ventilator-free Days up to Day 28

A participant is considered ventilator-free on a day if they meet the definition for being alive and not invasively mechanically ventilated in Section [5.4.1.3](#).

Intermittent data is expected after discharge from investigator site, therefore if participants have discontinued ventilation and have been discharged to a non hospitalised residence, they will be considered to be ventilation-free during the intermittent timepoints.

5.4.1.11. Time to Resolution of Pyrexia (>48h) up to Day 28

Time from dosing (days) to first resolution of pyrexia (defined as the first day of a >48-hour period with temperature below thresholds below) up to (and including) Day 28:

Location	Pyrexia Threshold	Core Temperature Equivalent
Forehead	>36.3°C	>37.8°C
Axilla	>36.6°C	>37.8°C
Sublingual region	>37.2°C	>37.8°C
Rectum or Tympanic membrane	>37.8°C	>37.8°C
Pulmonary artery branch	>37.8°C	>37.8°C
Bladder	>37.8°C	>37.8°C
Esophagus	>37.8°C	>37.8°C
Nasopharynx	>37.8°C	>37.8°C
Brain	>37.8°C	>37.8°C
Other	>36.3°C (Minimum Pyrexia Threshold)	>37.8°C

Evaluated for all participants with pyrexia at baseline.

This endpoint will use a composite approach such that if the intercurrent event of death occurs (on or prior to Day 28), then time will be censored at the end of follow-up (Day 28), including those that had resolution of pyrexia prior to death.

5.4.1.12. Clinical Status Assessed Using an Ordinal Scale Assessed at Days 4, 7, 14, 28, 42, and 60

Clinical status assessed using an ordinal scale assessed at Days 4, 7, 14, 28, 42 and 60 see [Table 4](#).

5.4.1.13. Time to Improvement of at Least 2 Categories Relative to Baseline in Clinical Status up to Day 60

Time from dosing (days) to final improvement of at least 2 categories relative to baseline in clinical status (see [Table 4](#)) up to (and including) Day 60. Evaluated for all participants with clinical status greater than 2 at baseline.

Note: if a participant has an improvement of at least 2 categories relative to baseline but then progresses back to a less than 2 category improvement the participant has not had their final improvement of at least 2 categories.

This endpoint will use a composite approach such that if the event has not occurred prior to the intercurrent event of death (on or prior to Day 60), then time will be censored at the end of follow-up (Day 60).

5.4.1.14. Change in COVID-19 Signs and Symptoms up to Day 60

Participants change in COVID-19 signs and symptoms up to Day 60 relative to dosing will be analysed.

Unadjusted relative risks, risk differences and odds ratios will be calculated and presented with 95% confidence intervals. For odds ratios, if the proportions are below 2% in any treatment group then exact 95% confidence interval will be calculated by inverting two one-sided (equal-tail) exact tests that are based on the noncentral hypergeometric distribution. All other confidence intervals will use the Wald method. A 2-sided Fisher's Exact Test will be performed, and p-values will be presented.

5.4.2. Main Analytical Approach

5.4.2.1. Time to Event Endpoints

The following exploratory endpoints will be analysed using time to event analyses with a follow-up to Day 28:

- Time to invasive mechanical ventilation (if not previously initiated)
- Time to definitive extubation
- Time to resolution of pyrexia (for at least 48h)

The following exploratory endpoints will be analysed using time to event analyses with a follow-up to Day 60:

- Time to improvement of at least 2 categories relative to baseline in clinical status

The endpoints will be analysed as per Section 5.3.2.2

5.4.2.2. Binary Endpoints

The following exploratory endpoints will be analysed as binary endpoints:

- Invasive mechanical ventilation (if not previously initiated)
- Alive and not invasively mechanically-ventilated
- Improvement relative to baseline in SpO₂, FiO₂ and SpO₂/FiO₂ ratio
- Improvement of at least 2 points relative to baseline on SOFA score

Binary secondary endpoints will be analysed as per Section 5.2.2.

Additionally, for Invasive mechanical ventilation, the counts and proportion of participants for whom prone position was, and was not, used will be produced.

5.4.2.3. Ordinal Endpoints

The clinical status assessed using an ordinal scale assessed at Days 4, 7, 14, 28, 42, and 60 will be summarized using counts and proportions of the number of participants in each category of the ordinal scale and will be analysed using a proportional odds logistic regression model, adjusting for treatment, ordinal scale category at baseline and age group. The outcome of the model is an odds ratio, a confidence interval and p-value for the odds of improvement on the ordinal scale, where an odds ratio >1 indicates improvement in clinical status.

In addition a shift table from baseline to the clinical status at Day 4, 7, 14, 28, 42 and 60 including a row for improvement (defined as moving from a higher category to a lower category) will be produced and the proportion of participants in each category of the ordinal scale will be summarised at each visit using a stacked bar chart.

5.4.2.4. Continuous Endpoints

The following exploratory endpoints will be analysed as continuous endpoints:

- Change of Sequential Organ Failure Assessment (SOFA) score
- Change in SpO₂, FiO₂, and SpO₂/FiO₂ ratio

Continuous endpoints will be summarised using the trimmed means approach (Permutt, 2017) where the proportion of data to be trimmed will be determined by the amount of missing data due to intercurrent events as defined in Section 5.1.4.

Study withdrawal will be treated as a negative event if it occurs prior to one of the listed intercurrent events. If the subject has recovered (has one of the intercurrent events listed

within the endpoint definition) prior to withdrawal then they will be considered to be recovered post-withdrawal.

Missing data without reason (no accompanying intercurrent event or withdrawal) will be treated as missing at random and will not count towards the trimmed sample.

5.4.2.5. Count Endpoints

The following exploratory endpoints will be analysed as count data

- Oxygen-free days
- Ventilator-free days

Summary statistics of the number of days will be presented and the data will be analysed using negative binomial regression adjusting for clinical status at baseline and age group.

